11.3 Subject privacy

11.4 Data disclosure

11.5 Data safety and monitoring

11.6 Risk/benefit

11.6.1 Potential study risks

11.6.2 Potential study benefits

11.6.3 Risk/benefit assessment

## 1. Abstract

Telemedicine allows clinicians to utilize modern telecommunication technology to provide healthcare services to patients including remote symptom monitoring. Given the spread of COVID-19 both locally and globally, is crucial to adapt accordingly in order to safely provide vulnerable cancer patient populations with optimal care while minimizing risk of exposure to COVID-19. In this study, we will utilize remote monitoring of patients with cancer via weekly patient-reported outcome (PRO) collection through the Way to Health (W2H) smartphone application and step data through wearable Fitbit devices. Patients with incurable lung and gastrointestinal cancers will be recruited based on whether they receive their care in-clinic or remotely. They will respond to weekly phone-based symptom surveys and wear Fitbits that track step data. This data will be collated in a Palliative Care Assessment Dashboard (PROStep Dashboard) sent to clinicians prior to each oncology visit to help inform patient management. In this feasibility study, two arms of patients will be monitored with symptom surveys and Fitbits; the study will randomize these patients to either 1) receive text feedback or 2) receive no text feedback. A third arm of patients will be randomized to receive no feedback, symptom surveys, or Fitbit device. Clinicians for patients in each arm will receive the PROstep Dashboard. The study will determine feasibility of this monitoring approach, and compare patient adherence to symptom surveys and step data collection between the two intervention arms.

## 2. Overall objectives

The objective of the study is to assess the feasibility of remote symptom and activity monitoring of patients with incurable lung and gastrointestinal cancers, determine the clinical utility of these remote monitoring tools and compare adherence to the intervention based upon the feedback that patients receive.

## 3. Outcomes

### *3.1 Primary outcome*

Patient utility surveys will use a 5-point Likert scale for responses scored 1-5. The two co-primary outcomes will compare the scores for the following two questions, **measured at 6 months (or 3 months if the patient did not complete their 6 month survey)**, between **intervention patients** (Arms B + C) and **control patients** (Arm A).

- How well do you feel your oncology team understands your symptoms (e.g. nausea, vomiting, weight loss, etc.)?
- How well do you feel your oncology team understands your activity level and ability to function?

### *3.2 Secondary outcomes*

The following secondary outcome will compare the same questions:

- **Measured at 3 months**, between **intervention patients** (Arms B + C) and **control patients** (Arm A).

We will compare cumulative adherence for patients in the intervention group (arm B and arm C). Each week, adherence will be defined as each week where the patient submits the weekly survey (i.e. adherence to PRO) and has step data for 4 of 7 days of the week (i.e. adherence to Fitbit platform), divided by the total number of weeks that the patient is enrolled in the trial.

- Comparison of mean patient adherence at three months for patients in arm B vs arm C
- Comparison of mean patient adherence at six months for patients in arm B vs arm C

We will analyze trends in the PROStep data (PRO surveys and Fitbit step data).

- Comparison of PRO scores between patients in arm B vs. arm C. These will be measured using mean and median composite symptom scores as reported by patients in their PRO surveys. The composite score is the sum of the scores for each domain in the PRO survey, and the mean or median composite symptom score is the mean or median of all composite scores collected during the study.
- Fitbit step data will be measured using mean daily step counts for all days in which Fitbit data is collected. Days where the patient does not have Fitbit data will be excluded from these calculations.

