## 5. Study design

### 5.1 Design

[figure not shown]
This prospective cohort study will evaluate the effect of remotely collected PROs and step data derived from wearable Fitbit devices, and remotely presenting those data to clinicians and patients at each oncology visit. We will enroll patients who are diagnosed with incurable lung or gastrointestinal cancer who are receiving (or planning to receive) chemotherapy. Eligible patients can have in-person or virtual visits with their oncology clinician prior to chemotherapy, which is of particular importance as many visits are now being done via telemedicine. Patients will be randomized into one of three arms – a control (arm a), an intervention with no patient feedback (arm b), and an intervention with patient feedback (arm c) – at a 1:1:1 allocation (**Figure 1: Patient Arms**). All intervention patients will receive 1) weekly PRO surveys for five symptoms administered through the W2H text platform and 2) a Fitbit wearable device that can track patient step, distance, active minutes, sleep, and heart rate data. At each subsequent medical oncology visit (either in-person or via telemedicine), oncology clinicians will receive a PROStep Dashboard that reports the patient’s 1) trends in the home-based PROs and step data, 2) acute care utilization in the prior six months (Oncology Evaluation Unit, emergency department or inpatient admissions), and 3) whether the patient has a documented Serious Illness Conversation (a type of Advance Care Planning note that is standard practice at PCAM). Arm C will receive a brief text message feedback including an active nudge question on their upcoming appointment.

Arm B will not receive text feedback. Arm A will receive no PRO surveys, Fitbit device, or patient feedback (arm a) (**Figure 2: Intervention by Patient Arm**). Patients will be enrolled for a total of six months, unless they disenroll earlier, and evaluated on the outcomes described above.

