### *5.4 Accrual*

The study sample will be drawn from patients who receive their cancer care from a GI or lung oncologist at the University of Pennsylvania's Perelman Center for Advanced Medicine (PCAM). We aim to enroll 125 patients. We anticipate enrolling these 125 patients over 6 months at a rate of 4 patients per week, a small fraction of the number of eligible patients with in-person or telemedicine visits at PCAM each week. A summary of recruitment mechanisms is found in Section 6 (Subject recruitment).

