## **9. Analysis plan**

For each primary outcome, we will compare the mean scores from the survey questions at 6 months (see section 3.1) for all 3 groups (2 intervention, 1 control) using a Kruskal-Wallis test with  $p < 0.05$  indicating statistical significance. If the result is significant, we will use the Tukey's honestly significantly difference (HSD) test to test pairwise comparisons. If the outcomes for any arm are skewed (not normally distributed), we will use log-transformation before applying all tests. For

clinicians who have completed a 3-month survey for a specific patient, but do not complete a 6-month survey for that patient, we will apply their 3-month survey responses in place of their missing 6-month survey for analysis for that specific patient. For example, if Clinician A completes a 3-month survey for Patient A, but not a 6-month survey, we will use the results from their completed 3-month survey in its place for Patient A (but not for other patients). That said, we will do a sensitivity analysis only using the coded 6 month analyses (complete case analysis).

We will repeat this analysis for the secondary outcome of composite survey score at 3 months. For patients who exit the study early, we will attempt to administer their next survey and use that assessment. These will be administered if patients have been enrolled for a minimum of 4 weeks of the enrollment period leading up to their following survey. For example, if a patient disenrolls 4 weeks after receiving their 3-month utility survey, they will be eligible for their 6-month survey whereas a patient who dis-enrolls at 3 weeks will not). If a patient dies or is otherwise unable to complete a survey, they will be omitted from the analysis for the relevant outcome. For patients who disenroll from the trial for any reason (voluntary, death, etc.), but meet this 4 week threshold, their clinicians will receive a utility survey. To assess whether responses in 3-month to 6-month surveys differ across arms, we will run an analysis of covariance (ANCOVA) model with the baseline score and arms as covariates, and change of score as the dependent variable.

We will use descriptive statistics to compare the secondary outcomes of adherence rates between the two intervention groups and trends in PROstep data. We will use Kruskal-Wallis tests for continuous outcomes and chi-square tests for categorical variables to compare these outcomes between all arms at 3 and 6 months.

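### Mean daily steps treat every day with any Fitbit data as a full day, so the means run low and would carry any wear difference between arms B and C

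*Combined protocol and SAP*

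**What the plan says.** Section 3.2 defines the step outcome as "mean daily step counts for all days in which Fitbit data is collected", and adds: "Days where the patient does not have Fitbit data will be excluded from these calculations". The only other day-level rule in that section belongs to adherence: a week counts if the patient submits the survey and "has step data for 4 of 7 days of the week". That rule also asks only whether data are present, and it is not linked to the step mean.

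Section 9 says: "We will use descriptive statistics to compare the secondary outcomes of adherence rates between the two intervention groups and trends in PROstep data". It then adds: "We will use Kruskal-Wallis tests for continuous outcomes". It contains no wear threshold or wear adjustment.

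Section 5.1 describes the device as "a Fitbit wearable device that can track patient step, distance, active minutes, sleep, and heart rate data". It gives no Fitbit to arm A. Section 8.3 tells participants to keep the device on as far as they can, at night too, without a minimum number of hours. Under the active nudge heading, it gives text feedback on step count to arm C only. Section 3.3 plans to correlate step and heart rate trends with performance status, hospitalization and survival.

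**The concern.** A step total is interpretable as activity only if the device was on the wrist for most of the waking day. Under the rule in Section 3.2, a morning of wear followed by a day on the charger enters the mean as a low-activity day at full weight. What counts as a day with data is also left open: it is unclear whether a synced day with zero steps, or a day with only sleep or heart rate data, is included.

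Two things are at stake. First, the level of the mean is too low in any arm where some included days are partial. Second, arm C differs from arm B by text feedback, and Section 2 makes it an objective to compare adherence according to the feedback received. A trial that asks whether feedback changes use of the device should not have a step measure that mixes device use with walking. Because arm A has no device, B versus C is the only between-arm step comparison that can be made. The correlations in Section 3.3 have the same weakness: if sicker patients wear the device for fewer hours, part of an association between steps and survival would be an association between wear and survival.

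**Working it through.** The documents give no step mean, standard deviation, power figure or wear data, so there is no figure of the plan's own to reproduce. What follows is an illustration.

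**Inputs from the documents.** The target in Section 5.4 is "We aim to enroll 125 patients", and Section 5.1 allocates 1:1:1, so 125/3 = 41.7; I use n = 41 per arm. The 0.05 level is stated in Section 9 for the primary outcomes and is assumed to carry over.

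**Assumed inputs.** True mean μ = 4,000 steps per day in both arms; between-patient SD of 2,000 or 2,500; p = share of included days with partial wear; c = share of a day's steps captured on such a day. The outcome is taken as a mean per patient.

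**Formulas.**
- Expected observed mean = μ × (1 − p × (1 − c)).
- Spurious C minus B difference d = μ × (1 − c) × (pB − pC).
- Standard error = SD × √(2/41), which is about 442 for SD 2,000 and 552 for SD 2,500.
- Chance of a two-sided rejection with no true difference = Φ(−1.96 + d/SE) + Φ(−1.96 − d/SE).

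**Numbers for the main case.** Arm B at 20%: 4,000 × (1 − 0.20 × 0.5) = 3,600. Arm C at 10%: 4,000 × (1 − 0.10 × 0.5) = 3,800. The difference is 200 steps, or 5% of the true mean.

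| Partial wear, B / C | c | Mean B | Mean C | d | d as % of 4,000 | Rejection, SD 2,000 | Rejection, SD 2,500 |
|---|---|---|---|---|---|---|---|
| 20% / 20% | 0.5 | 3,600 | 3,600 | 0 | 0% | 5.0% | 5.0% |
| 20% / 10% | 0.5 | 3,600 | 3,800 | 200 | 5% | 7.4% | 6.5% |
| 30% / 10% | 0.5 | 3,400 | 3,800 | 400 | 10% | 14.8% | 11.2% |
| 30% / 20% | 0.7 | 3,640 | 3,760 | 120 | 3% | 5.8% | 5.5% |
| 40% / 10% | 0.3 | 2,880 | 3,720 | 840 | 21% | 47.7% | 33.1% |

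The last two rows are the ends of the range examined (c from 0.3 to 0.7, gaps in p of 10 to 30 percentage points). Simulation of the Kruskal-Wallis test on log-normal patient means (SD 2,500, 4,000 replicates) gave 4.7% with equal partial wear at 20% and c = 0.5, 13.1% for 30% versus 10% at c = 0.5, and 50.7% at the extreme setting in the last row.

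**Reading the table.** The first row separates the two effects: equal partial wear lowers both means by 10% but creates no difference between arms. A spurious difference needs unequal partial wear. Its sign follows the sign of pB − pC, so if arm C had more partial wear than arm B the same figures would apply with C lower. If partial days were removed, and partial wear were unrelated to true activity, d would return to 0 and the rejection rate to about 5%.

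**The case against.** The strongest reply is that nothing in the documents shows unequal wear. Section 8.3 tells participants to wear the device as continuously as they can, sends reminders to wear and to sync, and has the coordinator call after two weeks without step data. None of this is described as differing between arms B and C. The one step message quoted for arm C tells the patient that steps have worsened since the previous week; it could shorten wear as easily as lengthen it. A reader might infer that the B versus C step comparison is confounded with wear, in arm C's favour. The documents do not support that: they give neither a wear difference nor a direction. This part of the objection stands, and the between-arm effect must be stated as conditional.

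It is also fair that the step bullet does not name the arms, that Section 9 promises descriptive statistics for these trends, and that no step hypothesis or decision rule appears. The B versus C comparison is inferred from the neighbouring bullet and from arm A having no device. Whether the Kruskal-Wallis sentence extends to steps is a matter of reading, so the rejection rates above matter only if it does.

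Finally, a valid-day rule has faults of its own. Because patients wear the device in bed, a cut-off on total heart rate hours could be met largely overnight: ten hours could be a night plus two waking hours. Excluding days by wear after randomisation may also select better days, if patients take the device off when they feel worst. Both points stand and shape the fix.

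What the objection does not remove is the rule itself. Reminders and instructions do not define a valid day, and partial days still enter at full weight.

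**Conclusion.** The concern holds in a limited form. As Section 3.2 is written, partial-wear days count as full days, so mean steps are biased low in each arm in which such days occur. If partial wear differs between arms B and C, part of any step difference would be wear, and the planned analysis could not tell the two apart. That second step is plausible but not shown.

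The 200- and 400-step figures (5% and 10% of an assumed 4,000) rest wholly on assumed steps, capture and wear. At 200 steps, the false rejection rate would be only 6.5% to 7.4%. The rates near 50% need 40% versus 10% partial wear with 30% capture, and should not be read as a forecast.

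The reach is a secondary, mainly descriptive outcome and the exploratory step correlations. The co-primary survey scores do not depend on it. This is a low-cost improvement, not a threat to the trial's main conclusion.

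**What to change.** In Section 3.2, state what makes a day one with Fitbit data, including how zero-step days and days with only sleep or heart rate data are handled. Then, before any look at step data by arm (no blinding is described, so unblinding cannot serve as the marker):

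1. Define a valid day by waking-hours wear, for example at least 10 daytime hours with recorded heart rate, with 8 and 12 hours as sensitivity versions. These cut-offs are assumptions.
2. Confirm first that heart rate is stored at hourly resolution or finer. Section 5.1 says only that the device can track it. If it is not, use a minimum-step rule, and acknowledge that this selects on the outcome itself and may drop days that were truly inactive.
3. Report the valid-day mean beside the planned all-days mean, with wear time and number of valid days by arm.
4. Repeat the step correlations of Section 3.3 on valid days.

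The cost is analysis time and a check of the stored data; there is no new visit, device or patient task. The downsides are that fewer days enter the mean, the cut-off is a convention, and exclusion by post-randomisation wear may select better days. For that reason both means should be shown and neither should replace the other.

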### 3.3 Exploratory outcomes

- The following exploratory outcomes will make the following comparisons for responses to the two questions in the primary outcomes:
  - Measured at 6 months (or 3 months if the patient did not complete their 6 month survey)
    - Between Arm B and Arm A
    - Between Arm C and Arm A
    - Between all Arms.
  - Measured at 3 months:
    - Between Arm B and Arm A
    - Between Arm C and Arm A
    - Between all Arms.
- Number of palliative care consults
- Number of documented advanced care planning (ACP) notes
- Number of documented serious illness conversations (SIC)
- Correlation between step, heart rate, distance, pace, elevation and sleep data trends, patient reported outcomes, patient and clinician ECOG assessment, and patient hospitalization and survival

- We will report descriptive statistics for the remaining questions on the patient utility surveys (mean and standard deviation) followed by t-tests between each individual arm and between all intervention patients (Arms B + C) and control patients (Arm A). Patient utility surveys include the following (the intervention arms receiving additional questions):
  - How well do you feel that your oncology team has addressed your symptoms?
  - How well do you feel that your oncology team has addressed your activity level and ability to function?
  - I feel that the PROStep data prompted better communication with my oncology team about my symptoms. **(arm b and arm c)**
  - I feel that the PROStep data prompted better communication with my oncology team about my activity level. **(arm b and arm c)**
  - My oncology team has discussed the PROStep data during my appointments. **(arm b and arm c)**
  - I feel that the PROStep data changed how my oncology team addressed my symptoms and/or ability to function. **(arm b and arm c)**
  - I feel that the PROStep data changed my oncology team's treatment of my cancer, such as decisions to start, continue, or stop cancer treatments like chemotherapy. **(arm b and arm c)**
  - I feel that the PROStep data triggered discussions with my oncology team about my prognosis or goals of my cancer care. **(arm b and arm c)**
  - I feel that regularly wearing my Fitbit is burdensome. **(arm b and arm c)**
  - I feel completing my weekly symptom surveys is burdensome. **(arm b and arm c)**
  - On a scale of 0-10, how likely is it that you would recommend PROStep to other patients with cancer? **(arm b and arm c)**
- The utility to clinicians will be measured using survey data at three and six months. These similarly use a 5-point Likert scale (1-5) and we will report descriptive statistics for this survey data. Clinician survey questions include:
  - To what extent was the information provided in the PROstep Dashboard helpful for you to better understand:
    - your patient's symptoms?
    - your patient's functional status?
  - To what extent did the PROstep dashboard change your management of the patient?
  - To what extent did the PROstep dashboard prompt you to have goals of care conversations with this patient?
  - To what extent did the PROstep dashboard have any adverse effect on the patient?
  - Please indicate any ways that the PROstep dashboard has been useful or harmful in the management this patient (open ended)

## 4. Background

Patients with incurable lung and non-colorectal gastrointestinal (GI) cancers benefit from earlier palliative care interventions. Early palliative care in patients with incurable lung and GI cancers has been shown to improve quality of life, reduce anxiety and depression, decrease end-of-life utilization, and possibly improve survival. Furthermore, PROs such as shortness of breath, weight loss, and appetite loss are independently associated with higher mortality in incurable lung and GI cancers. Limited life expectancy has been recognized as a potential trigger for early palliative care interventions. Improved identification of patients at risk of short-term mortality using patient-generated health data (PGHD) may allow better targeting of palliative care interventions to improve quality-of-life in incurable lung and GI cancers.

Recently available PGHD may improve performance of mortality prediction algorithms, but is captured on a low-scale. PGHD are health-related data generated by a patient; they include routinely collected information about patient symptoms, functional status, and activity levels out of the clinic. PRO assessment may allow clinicians to identify patients with high symptom burden or functional status decline who would also benefit from timely palliative care interventions. Regular PRO assessment in oncology has been associated with improved health-related quality of life and survival. Passively collected step counts and activity levels are proxies for functional status. In large prospective cohort studies of patients with cancer, both higher PRO scores for depression, fatigue, and pain and lower daily step counts have been independently associated with lower overall survival. While PROs and activity levels may be independently associated with prognosis, collection may be infeasible for large populations of patients. PROs may be collected via paper surveys, automated telephone systems, tablets or downloadable applications. Step counts and activity levels are usually passively collected via accelerometers (ex. Fitbits). However, there are few examples of large-scale collection of PRO or accelerometer data due to low response rates, inadequate resources, and suboptimal clinician and patient training.

## 5. Study design

### 5.1 Design

[figure not shown]
This prospective cohort study will evaluate the effect of remotely collected PROs and step data derived from wearable Fitbit devices, and remotely presenting those data to clinicians and patients at each oncology visit. We will enroll patients who are diagnosed with incurable lung or gastrointestinal cancer who are receiving (or planning to receive) chemotherapy. Eligible patients can have in-person or virtual visits with their oncology clinician prior to chemotherapy, which is of particular importance as many visits are now being done via telemedicine. Patients will be randomized into one of three arms – a control (arm a), an intervention with no patient feedback (arm b), and an intervention with patient feedback (arm c) – at a 1:1:1 allocation (**Figure 1: Patient Arms**). All intervention patients will receive 1) weekly PRO surveys for five symptoms administered through the W2H text platform and 2) a Fitbit wearable device that can track patient step, distance, active minutes, sleep, and heart rate data. At each subsequent medical oncology visit (either in-person or via telemedicine), oncology clinicians will receive a PROStep Dashboard that reports the patient’s 1) trends in the home-based PROs and step data, 2) acute care utilization in the prior six months (Oncology Evaluation Unit, emergency department or inpatient admissions), and 3) whether the patient has a documented Serious Illness Conversation (a type of Advance Care Planning note that is standard practice at PCAM). Arm C will receive a brief text message feedback including an active nudge question on their upcoming appointment.

Arm B will not receive text feedback. Arm A will receive no PRO surveys, Fitbit device, or patient feedback (arm a) (**Figure 2: Intervention by Patient Arm**). Patients will be enrolled for a total of six months, unless they disenroll earlier, and evaluated on the outcomes described above.

